Assessing the appropriate levels of physical activity is a challenge in healthcare currently. Physical inactivity is linked to 10% of premature mortality and is the fourth leading cause of death globally.² The benefit of physical activity in children is well defined: obesity prevention,^{3,4} reduction of cardiovascular risk factors,^{5,6} normal growth and development,^{7,8} depression prevention,⁹ reduction in risk of chronic diseases, health-related quality of life.¹⁰ The American guideline recommends 60 minutes per day of moderate-to-vigorous physical activity.¹¹ However, there is a lack of standardized measures of gait and physical activity, and more accurate measures are needed.

There is a significant growth and interest in wearable accelerometry devices that can measure various gait and activity metrics. The ActiGraph device has been investigated in several studies involving children age from 2 to 18.¹²⁻¹⁸ Despite this growing interest, only a few studies have focused their objective on assessing the feasibility of implementing these types of devices.^{19,20} Also, little is known about how children and parents accept the devices and perceive their usability and comfort.²¹

The rationale for this study is to compare gait quality metrics collected using the ActiGraph devices, APDM devices and GAITRite® walkway, during in-lab sessions (in the PfiRe Lab). APDM and GAITRite® walkway are used as reference comparators. GAITRite® is a pressure-sensitive walkway, which records gait metrics. APDM is a set of 6 devices that collect gait metrics. Both devices are used during in-lab assessments, but the deployment of these devices at home is impractical and not feasible. Hence the needed validation study of the ActiGraph device to measure for gait metrics continuously in a home environment.

In addition to the ActiGraph device studied in Cohort A, Cohort B of the study aims to evaluate the feasibility of the Panoramic Bracelet and associated algorithms such as SleepPy and GaitPy compared to the GENEActiv device and to evaluate the comfort and wearability of the Panoramic Bracelet. The results of this study will enable the use of novel devices in future clinical trials measuring scratch and sleep.

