Cohort B of the study aims to evaluate the feasibility of the Panoramic Bracelet device and associated algorithms compared to the GENEActiv device and to evaluate the comfort and wearability of the Panoramic Bracelet device.

The primary, secondary and tertiary/exploratory objectives for Cohort B of study and their respective endpoints are listed below.

Primary Objective(s):	Primary Endpoint(s):

 Evaluate the Panoramic Bracelet device and associated algorithms in the quantification of physical activity (eg sleep), scratch, and wear time, as compared to another accelerometry device (GENEActiv) during the at-home period. 	
 Sleep and scratch endpoints, and wear time compliance (~ days 8-15)

 To evaluate the participant's or caregiver's perception of wearability and comfort of 	
 At-home Panoramic Bracelet device wearability/comfort questionnaire responses

Panoramic Bracelet device during the at home monitoring period	from at-home monitoring period (this is Day 7+2, only 1 wrist).
Secondary Objective(s):	Secondary Endpoint(s):

To assess the compliance in wearing the Panoramic Bracelet device at home.To compare gait quality metrics collected using Panoramic Bracelet devices, APDM devices and GAITRite® walkway, during in-lab sessions.	
Number of hours per day wearing the device (only Panoramic Bracelet Days 1-7)Gait metrics defined in the Annex 2 (eg, gait speed, stride length) measured by APDM devices, GAITRite® walkway and Panaromic Bracelet devices (extracted with GaitPy algorithm).
Tertiary/Exploratory Objective(s):	Tertiary/Exploratory Endpoint(s):

To evaluate the participant's or caregiver's perception of wearability and comfort of Panoramic Bracelet device in-lab sessions.To evaluate the effect of floor surface (carpet vs tile) on gait metrics collected using Panoramic Bracelet and APDM devices.	
In-lab Panoramic Bracelet wearability/comfort questionnaire responses from Visit 1 (Day 1) (wrist and lumbar)Gait metrics defined in the Annex 2 (eg, gait speed, stride length) measured by Panoramic Bracelet and APDM devices across different floor surfaces.

RESEARCH METHODS

Study Design

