1. Evidence of a personally signed and dated informed consent document indicating that the participant and/or a parent/legally acceptable representative (LAR) has been informed of all pertinent aspects of the study. When there are 2 LAR, consent should be obtained from both of the child's LAR if present when the informed consent document is signed. When the participant is an emancipated minor with proven documentation present for review, consent should be obtained from the participant only.
2. Evidence of a personally signed and dated assent, indicating that the participant understands the nature of all pertinent aspects of the study, and is willing to participate in the study activities, if applicable, as consistent with the participant's age and ability to provide assent (verbal assent for children 3 to 5 years old, written assent for children 6 to 17 years old).
3. The participant (to degree appropriate for age) and parent/legally acceptable representative are able to understand, are willing and able to comply with protocol

requirements, scheduled visits, and other study procedures, and are likely to complete the study as planned.

4. Qualified male or female participants aged 3 to 17 years old inclusive. Qualified is defined as no significant health problems that would impair the completion of the physical activity tasks, does not carry any diagnosis of developmental delay and/or significant co-morbid medical conditions as determined by a medically qualified individual during medical history review with LAR and participant.
5. Children who are ambulatory.

Exclusion Criteria

Participants meeting any of the following criteria will not be included in the study:

1. Participation in other studies involving digital devices within 1 week and/or treatment with an investigational drug (Phases 1-4) within 30 days or 5 half-lives before the current study begins and/or during study participation. If the participant was enrolled in a trial with both digital devices and investigational drug, whichever time period is longest for exclusion (5 half-lives or 1 week) will be used.
2. Participants with implanted medical devices.
3. Minor participants who reach the age of majority during the study, as recognized under local law.
4. Participants whose parents/LAR are investigational site staff members directly involved in the conduct of the study and their immediate family members, site staff members otherwise supervised by the investigator.

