The participant will wear device under study (on the non-dominant wrist) for at least 2 weeks with some flexibility on the end date for scheduling the follow-up phone interview. They will be asked to wear the wrist device continuously. For the lumbar device (Cohort A only), they will be instructed to put on the device when they get up in the morning and remove when they go to sleep at night or nap during the daytime.

For Cohort B the participant will wear the Panoramic Bracelet device for approximately one week on the non-dominant wrist and at approximately Day 7 they will start wearing the

GENEActiv device on the same wrist until end of study. Both devices (Panoramic Bracelet and GENEActiv) will be worn at the same time. The position of the GENEActiv device and the Panoramic Bracelet device closeness to the wrist will be balanced per age group.

Approximately half the participants in each age group will wear the Panoramic Bracelet device proximal to the wrist and the GENEActiv device more distal to the wrist and vice versa See [Figure 2](#). A phone interview for the Wearability/Comfort questionnaire will be conducted at approximately Day 7.

[figure not shown]
The at-home monitoring will be performed outside the PfiRe lab without video monitoring or direct observation by site personnel.

[figure not shown]
[figure not shown]
The participant will complete an activity diary at home daily between Day 2 and Day 15 (Cohort A only).

For Cohort B the participant will complete an activity and sleep diary between Day 2 and Day 15

Any event with a device (issues with devices, loss of the devices, etc), the impact of this event and the action taken with device will be recorded anytime between Day 1 and Day 15+3 days in a device assessment CRF.

Figure 2. Wearable Sensor Device Locations on Participant At-home

COHORT NAME	DEVICE(S) [LOCATION OF DEVICE on body]	DESCRIPTION OF DEVICE(S)	DEVICE(S) XSENSORS CONFIGURATION ON BODY	HOME MONITORING
A	Lumbar and non-dominant wrist	ActiGraph CentrePoint Insight Watch		Yes ~15days

COHORT NAME	DEVICE(S) [LOCATION OF DEVICE on body]	DESCRIPTION OF DEVICE(S)	DEVICE(S) XSENSORS CONFIGURATION ON BODY	HOME MONITORING
B	Non-dominant wrist	Panoramic Wearable Bracelet		Yes ~15 days
B	Non-dominant wrist	GENEActiv Watch		Yes ~ Day 7 to 15

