The proposed sample size for this study is approximately 39 participants in each cohort (approximately 13 in each age group). To the best of our knowledge, no relevant data has been published before to validate accelerometry-measured gait metrics against GAITRite® walkway or APDM in pediatric population. Using data from X9001198 study (healthy adult participants, ages 18-40 and 65-85 years), the Intraclass Correlation Coefficient (ICC) between gait speed obtained from the sensor data vs gait speed obtained from the reference comparator gait mat was 0.72 (when corrected for a systematic bias of 0.17 m/s). The ICC value for the null hypothesis is derived by using the median value of the lower bound of ICC for all gait metrics (8 spatial and temporal metrics). ICC_{null} was 0.27, range = [0, 0.66]. In order to reach ICC value of 0.72 with ICC_{null} value of 0.27 using a one-tailed test with alpha = 0.05 and power = 0.8 it is estimated that at least 17 participants will be needed. Therefore, approximately 20 adult participants (anticipating 15% attrition) are required for the validation analyses. Here, we double the amount to roughly 40 participants to account for potential higher variance in the healthy pediatric participants (ages 3 – 17). Since we have 3 age groups, each group will equally have 13 participants, which results in a total of 39 participants.

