##### **3.1.2.2. Scratch Parameters**

- Total scratch duration (min.)
- Total scratch episodes (no.)

The scratch-related parameters for GENEActiv and Panoramic Bracelet will be derived by the ScratchPy algorithm.

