- For each day, accuracy of the sensor-derived metrics will be determined by computing the mean difference, mean absolute difference, variation of the difference, the mean percent error, the mean absolute percent error and the effect size between the Panoramic Bracelet device and GENEActiv (reference) device metrics.
- Box and whisker plots of digital metrics from the Panoramic Bracelet device and GENEActiv device will be plotted for each day.
- Bias, including the mean bias across days and bias from repeated measures, will be assessed by Bland-Altman plots and 95% limits of agreement between the Panoramic Bracelet device and GENEActiv device. Specifically, the following error measures will be computed: mean difference, lower and upper 95% limit of agreement. For assessing bias from repeated measures, both mean difference and 95% limits will be computed from the mixed effects model described above.
- Intra-class correlation coefficient (ICC) and its lower and upper confidence limits between metrics derived from the Panoramic Bracelet device and GENEActiv device will be computed, for mean/median/25% quantile/75% quantile across daily measures.
- Scatter plots of digital metrics from the Panoramic Bracelet device vs GENEActiv device with corresponding regression line and 95% CI will be plotted. The regression line and the 95% CI will be derived from the previous mixed effects model.

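### For the Cohort B scratch endpoints, the fixed ICC labels can reflect how much the enrolled children happen to scratch rather than how well the two devices agree

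*Protocol*

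**What the plan says.** **Endpoint.** The Cohort B objectives table in the protocol (Research Question and Objectives) places scratch with sleep and wear time among the primary endpoints. SAP 3.1.2.2 names two parameters, total duration in minutes and number of episodes: "The scratch-related parameters for GENEActiv and Panoramic Bracelet will be derived by the ScratchPy" algorithm.

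**Analysis.** SAP 6.2.1 states: "Intra-class correlation coefficient (ICC) and its lower and upper confidence limits between metrics derived from the Panoramic Bracelet device and GENEActiv device will be computed", using the mean, median and quartiles of each child's daily values. SAP 5.1 (Cohort B) adopts the Cohort A benchmarks: up to 0.4 poor, 0.4 to 0.59 moderate, 0.6 to 0.74 good, 0.75 to 1 excellent. SAP 6.2.1 also plans mixed models of association and of difference, Deming regression, absolute and percent errors, and Bland-Altman limits, including limits from the repeated-measures model.

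**Population.** Inclusion criterion 4: "Qualified is defined as no significant health problems that would impair the completion of the physical activity tasks", and the child "does not carry any diagnosis of developmental delay and/or significant co-morbid medical conditions". The Study Size section refers to "potential higher variance in the healthy pediatric participants". No criterion requires itch or skin disease.

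**Placement.** Under At-home Monitoring the bracelet is worn "on the non-dominant wrist and at approximately Day 7 they will start wearing the" GENEActiv on that same wrist.

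**Intended use.** The protocol's Rationale and Background says, and the SAP Introduction repeats: "The results of this study will enable the use of novel devices in future clinical trials measuring scratch and sleep". Study Size lists scratch agreement among the goals the sample will serve, but its only Cohort B planning input is total sleep time in adults.

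**The concern.** An ICC is the between-child variance divided by the total variance, so it describes the device and the sample together. A fixed label is useful only if the sample's spread resembles the spread in the intended setting. Here the setting named is trials that measure scratch, while the sample is children chosen for good health. If most of them scratch little, a sound device can be labelled poor. If one or two scratch a lot, the same device can be labelled excellent. Nothing in the plan states what scratch range is expected or how zero-scratch nights are to be shown, and the limitations section is silent on scratch. A reader planning a scratch trial could take either label at face value.

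**Working it through.** **Step 1. The plan's own figure.** Inputs from Study Size: ICC 0.88 against a null of 0.36, one-sided alpha 0.05, power 0.80, two devices (k = 2).

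- C0 = [1 + 2(0.36/0.64)] / [1 + 2(0.88/0.12)] = 2.125 / 15.667 = 0.1356, and (ln C0)² = 3.99.
- n = 1 + 2k(1.645 + 0.842)² / [(k − 1)(ln C0)²] = 1 + 4(6.18)/3.99 = 7.2, so 8.
- With 15% attrition, 8/0.85 = 9.4, so 10. Exact F-test power at 13 children is 96%.

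The stated 8, 10 and power above 95% reproduce. They are for sleep time; no scratch figure is given.

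**Step 2. Narrower spread with the planning error held fixed.** Scale the planning between-subject variance to 1, so the error variance is 0.12/0.88 = 0.136. If the between-child SD is a fraction f of the planning SD, ICC = f²/(f² + 0.136).

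| f | ICC |
|---|---|
| 1.00 | 0.88 |
| 0.75 | 0.81 |
| 0.50 | 0.65 |
| 0.25 | 0.31 |

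Solving for the benchmarks, the label leaves excellent below f = √(0.136 × 0.75/0.25) = 0.64 and becomes poor at f = √(0.136 × 0.40/0.60) = 0.30.

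**Step 3. In minutes of scratch.** The documents give no scratch distribution, so this step rests on assumptions: error SD 0.5 min per device in a child's mean, no bias, error constant over the range. ICC = s²/(s² + 0.25), with s the between-child SD.

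| s (min) | ICC | SAP label |
|---|---|---|
| 0.25 | 0.20 | poor |
| 0.5 | 0.50 | moderate |
| 1 | 0.80 | excellent |
| 5 | 0.99 | excellent |

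The limits of agreement are ±1.96 × √2 × 0.5 = ±1.39 min throughout, which follows directly from the constant-error assumption.

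**Step 4. Simulation without negative durations.** True scratch lognormal, error SD 0.5 min, values cut at zero, 39 children, 4,000 data sets per scenario, two-way absolute-agreement ICC.

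| Median true scratch (min) | Median ICC | Label | Half-width of limits (min) | Reference exactly zero |
|---|---|---|---|---|
| 5 | 0.99 | excellent in all | 1.37 | 0% |
| 0.5 | 0.39 | poor 52%, moderate 38% | 1.19 | 16% |
| 0.2 | 0.09 | poor 96% | 1.01 | 32% |

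Upward distortion: with all 39 children around 0.3 min the median ICC is 0.19. Setting one of them to 5 min raises it to 0.79, and to 10 min raises it to 0.94.

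The planned percent error cannot be computed where the reference value is zero, so the share of zeros matters for that measure too.

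**The case against.** Four points have weight.

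- **The low range is inferred.** A reader might conclude that scratch will sit at its floor. The documents do not show that: they give no scratch level, criterion 4 ties health problems to completing the activity tasks, and no skin condition is excluded by name. Low scratch is likely, no more.
- **The ICC does not stand alone.** The difference models, Deming regression and repeated-measures limits already planned would give a sound answer in natural units. This stands, and it is why the change is small.
- **The range would partly show.** Descriptive minimum and maximum, daily box plots and scatter plots are planned, and a log(x+1) transformation is allowed. A claim that nothing would reveal the range is therefore too strong. Missing are a zero-night table and a check on one influential child.
- **The illustration assumes constant error.** In Step 3 with a mean of 0.3 min (assumed), a between-child SD of 0.25 and an error SD of 0.5, a normal model puts about 30% of values below zero, which a duration cannot be. If error shrinks at low levels, the ICC falls less. Step 4 removes the negative values and the label still moves from excellent to poor. It also shows the limits narrowing near zero, so limits found at low scratch should not be carried to heavy scratchers either.

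What remains is that the labels have no fixed meaning for an endpoint whose range in this sample is unplanned.

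**Conclusion.** The point holds as a cheap improvement. It concerns the labels and the wording of the scratch conclusion. The agreement analysis as a whole is sound. The dependence of the ICC on spread is algebra; its size here rests on the assumed 0.5 min error and the assumed scratch distributions, since the documents supply neither.

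Three further inferences are tempting and are not supported:

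- **Single-wrist wear biases the comparison.** Both devices share the non-dominant wrist, with proximal and distal position balanced by age group, so dominant-hand scratching is missed by both. This limits statements about total scratch only.
- **At low levels the ScratchPy output is mostly false positives.** The protocol says only that the algorithm separates scratch from restless movement; no error rate is given.
- **A wrong label would trigger a wrong decision.** No decision rule or acceptance limit is tied to the ICC. Cohort B is framed as feasibility, and the protocol elsewhere says the study may potentially enable device use. The unqualified sentence on future scratch trials is the only claim that outruns the data.

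**What to change.** In SAP 6.2.1, for the two scratch endpoints only:

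1. Report the ICC with its confidence limits, and do not apply the SAP 5.1 labels.
2. Interpret the mean difference and repeated-measures limits of agreement already planned, in minutes per night and episodes per night, over the observed range.
3. Add the share of zero-scratch child-nights for each device, and a table of nights with both devices zero, one zero, or both positive.
4. Repeat the analysis without the highest-scratch child.

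In the protocol's Rationale and Background and the SAP Introduction, limit the scratch conclusion to agreement with GENEActiv on the non-dominant wrist over the scratch range observed in healthy children. Add the same statement to the protocol's limitations section.

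The cost is SAP wording, two small tables and one repeat run, with no new data. The ICC is still computed as the protocol specifies. The edits to the rationale and limitations change protocol text and so need a protocol revision. The price to the sponsor is a weaker claim about readiness for scratch trials.
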